### 2. Disease Characteristics

CRF: q\_studyentry

Variable Name	Values
d_stagemelanoma	Melanoma AJCC stage

### 3. Response to Therapy

CRF: q\_resp

Variable Name	Values
D_statover	Best response to therapy
DT_DTdisassess	Date best overall response
D_conf	Was response confirmed?

### 4. On-study Toxicities

CRF: q\_ae

Variable Name	Values
C_st	Flag for timing of AE (remove 0=baseline)
toxcode	CTCAE toxicity code
C_toxgrd	Toxicity grade
c_attrib	Relatedness to NeoVax (if 2, 3, 4 then deemed at least possibly related)

c_attribnivo	Relatedness to Nivolumab (if 2, 3, 4 then deemed at least possibly related)
c_attribipi	Relatedness to Ipilimumab (if 2, 3, 4 then deemed at least possibly related)
toxdesc	Text for toxicity name
toxcat	MEDRA System Organ Class
D_toxdlt	Was event a DLT?
COMM250	Description text for toxicities coded as "other"

Toxicities presented according to worst grade occurring per patient:

Proc sort data=tox; by subject toxcode descending c\_toxgrd;

```

data tox_unique;
set tox; by casenum toxcode;
if first.toxcode;
if index(toxdesc,"Other") gt 0 then toxdesc = propcase(COMM250);
run;

proc tabulate data=tox_unique format=6.1;
class toxcode toxdesc toxcat c_toxgrd/style={font_weight=bold};
table toxcat="System-Organ Class"*toxdesc = "Description",(all="Number patients"
c_toxgrd="Grade")*N/misstext="-";
run;

```

To select toxicities that are at least possibly related to therapy:

Subset to those events where c\_attrib\* is 2, 3, or 4.

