1.2 Primary Objective

- To evaluate the safety of administering Neoantigen Vaccine (Neoantigen Peptides plus Hiltonol and Montanide® ISA-51 VG) in combination with Nivolumab and locally administered Ipilimumab

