5.4.3 Definition of evaluable participants

All participants receiving at least one dose of Nivolumab will be evaluable for toxicity. Participants will be evaluable for immunologic activity if they have received all vaccinations during the priming phase and the first boost vaccination.

Participants with unresectable and measurable disease who have received at least one dose of study vaccine therapy will be considered evaluable for determination of tumor response.

A minimum of 2 vaccinations and absence of DLTs are required for a participant to complete the

6-week DLT observation period successfully.

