6. EXPECTED TOXICITIES AND DOSING DELAYS/DOSE MODIFICATIONS

Dose delays and modifications will be made as indicated in the following table(s). The descriptions and grading scales found in the revised NCI Common Terminology Criteria for Adverse Events (CTCAE) version 5.0 will be utilized for dose delays and dose modifications. A copy of the CTCAE version 5.0 can be downloaded from the CTEP website http://ctep.cancer.gov/protocolDevelopment/electronic_applications/ctc.htm.

If possible, symptoms should be managed as needed. In the case of toxicity, appropriate medical treatment should be used.

All adverse events experienced by participants will be collected from the time of the first dose of study treatment (first Nivolumab administration), through the study and until the final study visit. Participants continuing to experience toxicity at the end of treatment visit may be contacted for additional assessments until the toxicity has resolved or is deemed irreversible.

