Blood draw for immune response monitoring			X ^d	X ^d		X ^d			X ^d
Neoantigen vaccine administration		X				X		X	
Ipilimumab administration		X				X		X	
Vaccine site skin biopsy						X ^c			

a Leukapheresis procedure will be performed at the following timepoints:

- within 14 days before first vaccination timepoint #1
- within 7 days before vaccination timepoint #4

At each Leukapheresis collection timepoint 2x10 mL EDTA tubes will be collected. These tubes should be dropped off at the IAL upon collection

NOTE: If Leukapheresis cannot be performed a total of 200mL of blood should be drawn. If starting of vaccine administration gets delayed, week 20 leukapheresis will be collected before vaccination timepoint #4.

b Tumor biopsies will be collected at the following timepoints:

- within two weeks before starting the neoantigen vaccine Dose #1
- within two weeks prior to neoantigen vaccine Dose #4
- at the time of progression

At a minimum, 5 core biopsies or a surgical tumor specimen of 100mm³ will be obtained. Skin punch biopsies of a skin lesion are also allowed

c Expected neoantigen vaccine administration timepoints (see below). If there is a delay in vaccine preparation, Dose #1 should be administered as soon as the neoantigen vaccine is available. Doses #2, #3, and #4 should be scheduled every 3 weeks after Dose #1:

- neoantigen vaccine Dose #1: Week 12
- neoantigen vaccine Dose #2: Week 15
- neoantigen vaccine Dose #3: Week 18
- neoantigen vaccine Dose #4: Week 21.

If neoantigen vaccine administration coincides with nivolumab administration, neoantigen vaccine + Ipilimumab will be administered before Nivolumab

d Unless otherwise specified, 80 ml of blood will be drawn for immune monitoring. Blood collections will be performed at the following timepoints:

- one week (+/- 3 days) after neoantigen vaccine Dose #1
- before neoantigen vaccine Dose #2
- before neoantigen vaccine Dose #3
- within 3 weeks (+/- 3 days) after neoantigen vaccine Dose #4
- before each nivolumab administration during the post vaccination period

e Skin biopsies near vaccine injection sites (two 5 mm punch biopsies) should be performed at the following timepoints:

- prior to neoantigen vaccine Dose #3,
- between 48-72 hours after neoantigen vaccine Dose #3

Additionally, if a different vaccine site appears to clinically have a higher degree of inflammation, additional punch biopsy (two 5mm) of that site may be taken.

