**DFCI Protocol #: 18-279**

**Statistical Analysis Plan**

**November 20, 2023**

**Design:** The study is an open label, phase Ib trial in which patients with stage III B/C/D or stage IV melanoma were treated with NeoVax plus Montanide® ISA-51 VG in combination with nivolumab and locally administered ipilimumab. Tumor from a surgical resection specimen or core needle biopsy of a melanoma metastasis was used to prepare DNA and RNA for sequencing. Patients began treatment with nivolumab, and vaccine was prepared during the initial 12 weeks of nivolumab therapy. At week 12, patients began vaccination with up to 20 neoantigen peptides. These peptides were encoded by non-silent mutations that were identified through DNA and RNA sequencing. Up to 20 peptides of approximately 20 amino acids in length were prepared for each patient and were administered together with the immune adjuvant poly-ICLC and Montanide® ISA-51 VG, a mineral oil-based immune adjuvant analogous to incomplete Freund's adjuvant (IFA).

Concurrently with the vaccine and nivolumab, ipilimumab was delivered via subcutaneous injection in proximity to each vaccination site to 1) direct anti-CTLA-4 activity to the vaccine-draining lymph nodes, and 2) limit systemic toxic effects. This approach has been shown to be effective in animal tumor models and was expected to result in significantly reduced levels of systemic ipilimumab compared to the approved dose/schedule in advanced melanoma (3 mg/kg q3wks for four doses in the metastatic setting). The ipilimumab dose would be escalated/de-escalated from 2.5 mg/kg flat dose per injection in Cohort 1. Serial tumor biopsies and vaccine site biopsies were performed as shown in the schema below.

The primary endpoint is the rate of DLTs (CTCAE V5.0), as outlined and defined in Section 5.5 of the protocol. We chose dose escalation cohorts of five patients, rather than a more traditional 3+3 design, because the determination of whether to treat at a different dose in this trial was made over a longer period due to the time needed for vaccine preparation and the extended period for safety evaluation. Three dosing cohorts were considered, each varying the dose of ipilimumab. The decision rule to escalate to the next dose was based on having zero or one patient (out of five) experiencing a DLT during the first 42 days of vaccine therapy. The first cohort, Cohort 1, was treated with Ipilimumab 2.5 mg per injection site.

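### The SAP's adverse event table pools the nivolumab-only run-in with the vaccine plus local ipilimumab period, and pools the ipilimumab dose levels

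*SAP*

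**What the plan says.** **Tabulation (SAP section 4, On-study Toxicities).** The timing variable C_st is described only as "Flag for timing of AE (remove 0=baseline". The code sorts by descending grade, keeps one record per patient and toxicity code, and tabulates with "class toxcode toxdesc toxcat c_toxgrd/style={font_weight=bold". No period, cohort or dose-level variable appears. Related events are those where c_attrib* is 2, 3 or 4. Three relatedness variables exist, one each for NeoVax, nivolumab and ipilimumab. DLTs have a separate flag, D_toxdlt.

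**When collection starts (Protocol section 6).** "All adverse events experienced by participants will be collected from the time of the first dose of study treatment (first Nivolumab administration").

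**When the combination starts.** The SAP's design paragraph says "Patients began treatment with nivolumab, and vaccine was prepared during the initial 12 weeks of nivolumab therapy", and then "At week 12, patients began vaccination with up to 20 neoantigen peptides". The Protocol's Study Calendar allows a later start: "If there is a delay in vaccine preparation, Dose #1 should be administered as soon as the neoantigen vaccine is available".

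**Who is counted (Protocol 5.4.3).** "All participants receiving at least one dose of Nivolumab will be evaluable for toxicity".

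**What the table is for.** The primary objective (Protocol 1.2) is the safety of the vaccine "in combination with Nivolumab and locally administered Ipilimumab". The SAP's primary endpoint entry says adverse events were recorded to describe the safety and side-effect profile of NeoVax. For best response the SAP states a per-cohort denominator; for toxicity it states none.

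**The concern.** Events before the first vaccination cannot have been caused by the vaccine or by local ipilimumab. Yet the printed method puts them in the same cells as events on the combination. Three features add to this:

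- The worst grade is taken over all non-baseline time. A severe run-in event therefore replaces a milder event of the same type after vaccination, and a reader of the table cannot recover it.
- Protocol 5.10 lists failure to produce enough acceptable vaccine as a reason for leaving the study. Patients with nivolumab exposure only are therefore foreseeable, and they are in the evaluable set.
- Ipilimumab dose is the only factor varied between cohorts, and the table does not show it.

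At stake is the accuracy of the reported safety profile. Accrual stopped at the end of dose escalation, so there is no expansion cohort to dilute a misplaced event. Among about 10 patients, one patient moves an apparent rate by 1/10, or 10 percentage points.

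**Working it through.** **1. The plan's own figures.** The SAP's only design table gives the probability of 0 or 1 DLT in 5 patients, (1-p)^5 + 5p(1-p)^4. For true rates of 10, 20, 30, 40, 50 and 60% this gives 91.9, 73.7, 52.8, 33.7, 18.8 and 8.7%, matching the stated 92, 74, 53, 34, 19 and 9. The table depends only on DLT counts. Protocol 5.5 counts DLTs within 42 days of vaccine initiation, so run-in events do not enter it. The point below changes none of these figures.

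**2. What the tabulation rule does.** Consider five invented records, used only to trace the rule:

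| Patient | Dose level | Time | Event | Grade |
|---|---|---|---|---|
| 1 | 1 | baseline | fatigue | 1 |
| 1 | 1 | week 6, nivolumab only | rash | 3 |
| 1 | 1 | week 16, vaccine period | rash | 1 |
| 6 | 2 | week 8, nivolumab only | diarrhea | 3 |
| 7 | 2 | week 16, vaccine period | diarrhea | 2 |

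- Under the SAP's rule, the baseline record is dropped and the table shows rash grade 3 in one patient, diarrhea grade 3 in one and diarrhea grade 2 in one.
- Split by period and dose level, both grade 3 events are in the run-in. The vaccine period shows rash grade 1 at dose level 1 and diarrhea grade 2 at dose level 2. The pooled table had hidden the grade 1 rash.

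**3. Illustrative size.** The documents do not give the share of nivolumab toxicity that falls in the run-in, so a range is shown.

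- Rate r: treatment-related grade 3-4 events in 52 of 306 nivolumab patients, 17.0% (Protocol 2.3.5.2).
- Patients n: 10, inferred from two escalation cohorts of 5. The SAP does not state it.
- Share f of those events in the 12-week run-in (assumed). Even spread over the two-year maximum gives 12/104 = 12%. Even spread over the one-year maximum for resected disease gives 12/52 = 23%. Early clustering is represented by 50%.

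Expected patients = n × r × f. Probability of at least one = 1 - (1 - r × f)^10.

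| f | r × f | Expected patients | P(at least one) |
|---|---|---|---|
| 12/104 | 0.0196 | 0.20 | 18% |
| 12/52 | 0.0392 | 0.39 | 33% |
| 50% | 0.0850 | 0.85 | 59% |

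**4. Whether attribution separates the periods.** An event before any vaccine or ipilimumab should not be coded as related to either, so a subset on the NeoVax or ipilimumab variable would remove most run-in events. In the records above, with the two run-in events coded related to nivolumab only, a NeoVax-only subset returns just the two vaccine-period events. However, c_attrib* can also be read as any of the three variables. Under that reading the related-events table equals the pooled table. After vaccination starts, Protocol 7.8.1.4 and 7.8.1.5 list the same seven organ systems for nivolumab and ipilimumab, so attribution between those two drugs is a judgement between overlapping profiles.

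**The case against.** The strongest reply is that this is a supportive table and the printed code is only a skeleton. The code does not contain the stated baseline filter, and it sorts by subject but processes by casenum. A cohort table might be produced anyway. The non-zero codes of C_st are undefined and may already mark period. The part of the SAP just before Disease Characteristics was not available to me and may list a cohort variable. All this is fair and limits certainty. If baseline meant before vaccination, the run-in part of the point would fall, although Protocol section 6 makes first nivolumab the natural reading; the dose-level part would remain. As printed, the method uses neither period nor dose.

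Several stronger readings are tempting, and the documents do not support them:

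- *The primary endpoint is contaminated.* It is not. The DLT rate has its own flag and a window that starts at vaccination, and dose decisions rest on DLTs cohort by cohort.
- *Attribution gives no separation.* Three separate variables give partial separation, provided they are used separately.
- *About 1.7 patients are misplaced.* A reader could compute 10 × 0.17 = 1.7 and 1 - 0.83^10 = 84.5%. Those figures cover the whole nivolumab exposure, most of which may fall after vaccination starts.
- *A split table would show what the vaccine and ipilimumab add, or a dose trend.* With about five patients per dose level, no control arm and nivolumab exposure accumulating throughout, it can describe but not establish either. The documents plan no such comparison of general adverse events.

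**Conclusion.** The point holds for the descriptive safety profile. Followed as printed, the SAP's adverse event table mixes about 12 weeks of nivolumab-only experience, longer if vaccine is delayed, with the combination period. It includes any patients never vaccinated, merges the ipilimumab dose levels, and lets a worse run-in grade mask a vaccine-period event. This serves the table's stated purpose of describing NeoVax safety poorly.

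The likely size is modest: about 0.2 to 0.85 patients with a run-in grade 3-4 related event, and an 18% to 59% chance of at least one. This rests on n = 10, on an assumed run-in share of 12% to 50%, and on a 17.0% rate from melanoma, renal and lung cancer patients treated at several nivolumab doses. It also rests on reading baseline as before first nivolumab.

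**What to change.** 1. Define every value of C_st.
2. Using C_st or CRF dates, tabulate worst grade within period: (a) first nivolumab to before first vaccination; (b) first vaccination onward. First confirm that these sources identify the period, because the visible SAP lists no event onset or dosing date.
3. In (b), add columns by ipilimumab dose level and use vaccinated patients as the denominator. State the denominator for (a).
4. State that the related-events subset is shown separately for the NeoVax, nivolumab and ipilimumab attribution variables.
5. Keep the pooled table as supportive, and label all these tables as descriptive.

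The cost is a derived period variable, a dose-level class variable and a few more tables with sparser cells. If neither C_st nor the CRF dates identify period, that information would have to be recovered first. The design, the DLT analysis and the care of patients do not change. Period (b) will still contain the nivolumab continuation phase, which a footnote should say.

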## 5. Deaths and Overall Survival

CRF: q\_survival

Variable Name	Values
DT_DTDEATH	Month/day/year death
DT_DTCONT	Month/day/year last follow-up
C_STATUS	Patient status (death = 2)

## 6. Time to Progression

CRF: q\_resp

Variable Name	Values
C_STATOVER	Value = 5 for patients with PD
DT_DTPROG	Date of disease progression

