11.1.4.4 Evaluation of Best Overall Response

The best overall response is the best response recorded from the start of the treatment until disease progression/recurrence (taking as reference for progressive disease the smallest measurements recorded since the treatment started). The patient's best response assignment will depend on the achievement of both measurement and confirmation criteria.

For Participants with Measurable Disease (i.e., Target Disease)

Target Lesions	Non-Target Lesions	New Lesions	Overall Response	Best Overall Response when Confirmation Is Required*
CR	CR	No	CR	>4 wks Confirmation**
CR	Non-CR/Non-PD	No	PR	
CR	Not evaluated	No	PR	
PR	Non-CR/Non-PD/not evaluated	No	PR	>4 wks Confirmation**
SD	Non-CR/Non-PD/not evaluated	No	SD	Documented at least once >4 wks from baseline**
PD	Any	Yes or No	PD	no prior SD, PR or CR
Any	PD***	Yes or No	PD	
Any	Any	Yes	PD	

* See RECIST 1.1 manuscript for further details on what is evidence of a new lesion.
 ** Only for non-randomized trials with response as primary endpoint.
 *** In exceptional circumstances, unequivocal progression in non-target lesions may be accepted as disease progression.

Note: Participants with a global deterioration of health status requiring discontinuation of treatment without objective evidence of disease progression at that time should be reported as “*symptomatic deterioration*.” Every effort should be made to document the objective progression even after discontinuation of treatment.

For Participants with Non-Measurable Disease (i.e., Non-Target Disease)

Non-Target Lesions	New Lesions	Overall Response
CR	No	CR
Non-CR/non-PD	No	Non-CR/non-PD*
Not all evaluated	No	not evaluated
Unequivocal PD	Yes or No	PD
Any	Yes	PD

* ‘Non-CR/non-PD’ is preferred over ‘stable disease’ for non-target disease since SD is increasingly used as an endpoint for assessment of efficacy in some trials so to assign this category when no lesions can be measured is not advised

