Timelines: We expect to enroll one patient per month. We expect FPFV to occur by September 2020. LPFV is expected for July 2022 and overall duration of the study will be 4 years.

Analysis of Secondary Endpoints

Secondary endpoint in this clinical trial will: (a) assess the induction of IFN- γ T-cell response or tetramer staining to the assay peptides, and (b) to estimate rates of disease progression or recurrence (RECIST 1.1) depending on whether the patient is resected or has measurable disease. Analyses of the secondary endpoint will be based on 15 patients treated at the MTD.

The induction of IFN- γ T-cell response will be based on ELISPOT assessments taken prior to vaccine administration and at week 16. The proportion of patients who achieve more than 55 SFU/10⁶ PBMC or 3 times their baseline level will be presented with a 90% exact binomial

confidence interval. Based on a cohort of size 15, the confidence interval will be no wider than 0.46.

The proportions of patients with disease progression or recurrence, according to melanoma stage, will be presented with 90% exact binomial confidence intervals.

Analysis of Correlative Endpoints

Longitudinal analyses of PBMC immune response kinetics to the peptide pool and to individual epitopes will be presented graphically and descriptively at each time point. Changes in the magnitude of the response relative to pre-treatment at several different time points after vaccination will be summarized descriptively. Changes in response between pre-treatment and 16 weeks post-vaccination, which is the time of the primary immunologic endpoint, will be assessed using the Wilcoxon signed-rank test.

Immune studies of T cell subpopulations (CD4⁺, CD8⁺, central/effector memory cells, Th1/Th2 cells, T-reg, etc.), myeloid-derived suppressor cells (MDSC), CTL response, and T cell activation status will be summarized using descriptive statistics.

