### **Secondary Endpoints**

a. Best Response to Therapy

The number of patients with best response of CR or PR (per RECIST 1.1) will be summarized. For rate estimation, the denominator is the number of patients in each cohort.

b. Disease Progression/Recurrence

The number of patients with disease progression (unresectable) or disease recurrence (resectable).

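### The SAP marks progression with a field it labels as best response, so progression after disease control may go unflagged unless the event rule is stated

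*SAP*

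**What the plan says.** SAP section 3 (Response to Therapy, form q_resp) lists D_statover as "Best response to therapy" and pairs it with DT_DTdisassess, described as "Date best overall response". SAP section 6 (Time to Progression) draws on the same form and lists two variables: C_STATOVER, annotated "Value = 5 for patients with PD", and DT_DTPROG, described as "Date of disease progression".

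Secondary endpoint b in the SAP's Statistical Analyses is a count, "The number of patients with disease progression (unresectable) or disease recurrence (resectable", with no variable named.

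Protocol section 11.1.4.4 gives the rule for best response: "The best overall response is the best response recorded from the start of the treatment until disease progression/recurrence". In its table for measurable disease, the PD row carries the condition "no prior SD, PR or CR". Protocol section 13.1 plans the matching estimate: "The proportions of patients with disease progression or recurrence, according to melanoma stage, will be presented with 90% exact binomial confidence intervals".

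Four things are not stated in the SAP: what the C_ and D_ prefixes mean, whether q_resp holds one record per patient or one per assessment, how C_STATOVER and DT_DTPROG combine to define an event, and which field or code records recurrence in a resected patient.

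**The concern.** Best response and progression status answer different questions. A patient with stable disease at week 12 who progresses at week 36 has progressed, but the best overall response remains SD. A best-response field used as a progression flag therefore picks up only patients whose disease was never controlled. As long as code 5 means PD, the error runs one way: it can lower the count for secondary endpoint b but not raise it.

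The patients at risk of being dropped are those who first did well, and possibly the resected patients, for whom recurrence is the whole of the endpoint. The regimen could then appear to delay progression or recurrence because of how the event was coded.

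**Working it through.** The plan states no progression or recurrence figure, so there is none to reproduce. The check compares definitions and then illustrates the size.

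1. **Is it one field?** The stem (STATOVER) and the form (q_resp) match; only the prefix differs. Where the SAP shows values, C_ variables hold numeric codes: C_st (0), c_attrib (2, 3, 4), C_STATUS (2) and C_STATOVER (5). D_ variables such as D_toxdlt, D_conf and D_statover are described by a question or label without codes. That C_STATOVER is the coded form of D_statover is an inference, but the SAP's own naming supports it.

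2. **Which variable is the event indicator?** SAP section 5 (Deaths and Overall Survival) has the same layout: C_STATUS carries the event code (death = 2) and DT_DTDEATH supplies the date. By that parallel, C_STATOVER = 5 is the event in section 6 and DT_DTPROG dates it. No text makes a filled DT_DTPROG an event in its own right.

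3. **What does a best response of 5 identify?** Under protocol 11.1.4.4, with one best-response value per patient:
   - PD with no earlier SD, PR or CR: best response PD, flagged.
   - SD, PR or CR, then PD: best response SD, PR or CR, not flagged.
   - Completely resected, then recurrence: flagged only if the recurrence is coded 5, which the SAP does not state.

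4. **Size per missed event.** The SAP's Modified Design paragraph says that accrual stopped at the end of dose escalation. Two full cohorts of 5 give 2 × 5 = 10 patients, so one missed event changes the rate by 1/10 = 10 percentage points.

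5. **Illustration.** Assume n = 10 and 5 true events, of which k are not flagged. The flagged rate is (5 − k)/10. The interval is the exact 90% binomial type named in protocol 13.1. With x flagged, its lower limit is the 5% quantile of Beta(x, n − x + 1) and its upper limit is the 95% quantile of Beta(x + 1, n − x); the lower limit is 0 when x = 0.

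| Missed (k) | Flagged | Rate | Exact 90% CI |
|---|---|---|---|
| 0 | 5/10 | 50% | 22.2% to 77.8% |
| 1 | 4/10 | 40% | 15.0% to 69.6% |
| 2 | 3/10 | 30% | 8.7% to 60.7% |
| 3 | 2/10 | 20% | 3.7% to 50.7% |
| 4 | 1/10 | 10% | 0.5% to 39.4% |
| 5 | 0/10 | 0% | 0% to 25.9% |

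The 5 true events and each k are assumptions; the documents give neither.

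**The case against.** The strongest reply is that the SAP may already catch every event.

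- **The date field.** DT_DTPROG sits beside the flag in section 6. If it is filled for every patient who progresses and the analyst uses it, nobody is missed.
- **Record level.** The date paired with D_statover is named DT_DTdisassess, which fits one record per assessment. A 5 at any visit would then catch progression after SD or PR.
- **No stated link.** Section 6 is a list of data sources. The text of endpoint b does not say that its count uses C_STATOVER.
- **Recurrence as a new lesion.** Protocol sections 11.1.4.3 and 11.1.4.4 treat a new lesion as PD, so a recurrence could be coded 5. Protocol section 5.8 also requires progression found in follow-up to be recorded on a case report form.

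All four points stand, and together they make the undercount conditional. A reader might infer that late progressors and resected patients who recur will be counted as event-free; the documents do not establish that.

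A reader might also try to size the loss from the protocol's background figures, and this fails too. In section 2.3.5.4, 31% with a response and 7% with stable disease for 24 weeks or longer describe disease control under nivolumab alone, not later progression; several response durations there were still ongoing. In section 2.3.5.4's adjuvant study, recurrence-free survival of 70.5% at 12 months and 58% at 3 years counts deaths as well as recurrences. The documents also give no split of this trial's patients into resected and unresectable.

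The reply does not remove the need for a rule. If q_resp holds one record per assessment, the section 3 label needs a selection rule for best response that the SAP does not give. If DT_DTPROG defines the event, the SAP does not say so, and it gives no instruction for a patient with a filled date and a STATOVER value other than 5.

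**Conclusion.** The point holds as an event definition that fails on its own label, with a conditional risk of undercounting. Three assumptions lead to missed progression after SD, PR or CR: C_STATOVER is the coded form of D_statover, the field holds one best-response value per patient, and the event is taken from the flag rather than from DT_DTPROG. Missed recurrence in resected patients further requires that recurrence is not coded 5.

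If either the second or the third assumption fails, the undercount of progression after disease control can be zero. If all three hold, it equals the number of patients who progressed after SD, PR or CR, plus any resected patients whose recurrence was not coded 5. The documents do not give that number. At 10 percentage points per event with 10 patients, one or two such patients would visibly change the reported rate.

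The endpoint is secondary and descriptive, and the primary DLT analysis is unaffected. The listing that precedes SAP section 2 (Disease Characteristics) was not available to me, so a related definition there cannot be excluded. The rule should be settled before endpoint b is reported.

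**What to change.** In SAP section 6 and in secondary endpoint b of the Statistical Analyses, define the event as the first documented RECIST 1.1 progression in patients with unresectable disease, or the first documented recurrence in completely resected patients. Identify it by a non-missing DT_DTPROG, whatever the best response. This agrees with protocol section 5.9, which dates progression at the initial event even when nivolumab continues.

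Confirm that recurrences in resected patients populate DT_DTPROG. Use STATOVER for best response only. As a check, list every patient whose STATOVER value and DT_DTPROG disagree and resolve each case against the scan records.

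The cost is about one line of programming specification, on a field the SAP already lists, plus a short data check in about 10 patients. The downside is that the reported progression or recurrence count may rise.
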